4.0 STUDY DESIGN

4.1 Overall Design

This is a double-blind, randomized, placebo-controlled, multicenter study comprised of 3 phases: screening (up to 2 weeks [Day -15 to Day -2]), In-Clinic Treatment (Day -1 to Day 2; including double-blind treatment [Day 1]), and post-treatment follow-up (7 and 14 days after infusion, on Days 8 and 15, respectively). The study consists of 3 arms: placebo, PCN-101 Solution for Injection 30 mg, and PCN-101 Solution for Injection 60 mg. A total of 93 adult subjects with TRD will be randomly allocated in equal cohorts of 31 subjects/arm to the 3 arms of the study in a blinded manner. Randomization will be stratified by region (US, EU).

Subjects will be randomized within 14 days of screening (Visit 1). Subjects will be admitted to the clinic the evening prior to study treatment administration (Day -1, Visit 2) and undergo baseline testing to ensure continued study eligibility. Study treatments will be infused IV over 40 minutes the next morning (Day 1, Visit 2). Starting immediately prior to dosing, subjects will be monitored closely for safety. Additionally, the subjects' alertness, mood, and other psychological parameters will be assessed by clinician- and patient-completed scales and questionnaires. Subjects will be discharged no earlier than 24 hours postinfusion and after the final in-clinic assessments have been completed (Day 2, Visit 2). Subjects will be asked to return to the clinic approximately 6 days (Day 8, Visit 3) and 13 days (Day 15, Visit 4) after discharge to assess the safety and tolerability of the study treatments and to determine the durability of the antidepressant effect.

During the coronavirus disease 2019 (COVID-19) pandemic, the specific guidance from local public health and other competent authorities regarding the protection of individuals' welfare must be applied. If subjects cannot attend follow up visits in person because of restrictions arising as a consequence of the COVID-19 pandemic, the Investigator must discuss with the Medical Monitor potential mitigation.

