5.1 Inclusion Criteria

Subjects are eligible to be included in the study only if all of the following criteria apply:

1. Be capable of giving and give signed informed consent, which includes compliance with the requirements and restrictions listed in the Informed Consent Form (ICF) and in this protocol.
2. Be male or female 18 to 65 years of age inclusive at the time of signing the ICF.
3. Weigh ≥ 50 kg and have a BMI ≥ 18 and ≤ 35 .
4. Have a diagnosis of recurrent MDD without psychotic features per the DSM-V, confirmed by the MINI.
5. Have an HAM-D total score > 20 at screening and baseline (Day -1).
6. Have an inadequate response to at least 2 antidepressants in the current episode of depression that were each given for ≥ 6 weeks at an adequate dose as defined by the Massachusetts General Hospital Antidepressant Response Questionnaire (MGH-ATRQ).
7. Must be on stable oral antidepressant treatment without a dose change for at least 30 days before screening (a missed dose, or reasonable number of missed doses per Investigator's discretion, in that period does not exclude a subject).
8. A male subject must be medically confirmed sterile for at least 6 months prior to screening or agree to use highly effective contraception (see [Appendix 5](#)) during the treatment period and for at least 3 months after the last dose of study treatment and refrain from donating sperm during this period. If a male with a partner who is of childbearing potential (OCBP) is included, his partner also needs to use highly effective birth control measures.
9. A female subject is eligible to participate if she is not pregnant, not breastfeeding, and at least 1 of the following conditions applies:
 - Not of childbearing potential (see [Appendix 5](#)).
 - A subject OCBP who agrees to follow the highly effective contraceptive guidance (see [Appendix 5](#)) on highly effective birth control measures during the treatment period and for at least 3 months after the last dose of study treatment and refrain from donating eggs during this period.

10. Be medically stable on the basis of physical examination, medical history, vital signs, and 12-lead ECG performed at screening. If there are abnormalities, the subject may be included only if the Investigator judges the abnormalities not to be clinically important. This determination must be recorded in the subject's source documents and initialed and dated by the Investigator.

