The duration of the study will be up to 29 days per subject, which includes a screening period, an in-clinic visit, and 2 follow-up visits. A subject will be considered to have completed the study if he/she has completed all phases of the study including the second follow-up visit.

All disposition data will be presented in a listing format for the FAS. Subjects who failed screening will be presented in a listing format for the Screening Analysis Set.

B. Protocol Deviations

Major protocol deviations will be reviewed and determined prior to the unblinding of this study.

All deviation data will be presented in a listing format for the FAS.

C. Subject Characteristics

The subject characteristics defined below will be presented in summary tables using the most recent data collected prior to study drug dosing. No formal statistical comparisons will be performed.

All subject characteristic data will be listed by subject for the FAS.

Data collected for the following subject characteristics at Baseline will be summarized by treatment group. Race and ethnicity were not planned to be collected at the start of the study as the trial was originally held in Europe only, with local regulations preventing the collection of this data. With expansion of enrolment to US sites, it was determined by the Sponsor that it would be non-critical to include race and ethnicity in the analysis for this proof of concept study. As a result, no race or ethnicity data is collected in the study.

- Age (years)
- Age Category (18 to 44 years and 45 to 65 years)
- Sex (Male, Female)

- Region (US or EU)
- Baseline MADRS total score
- Baseline MADRS Score (<35, ≥35)
- Baseline HAM-D total score
- Body Mass Index (kg/m²)
- Duration of depression (years)
- Duration of depression (<5 years, 5 to 10 years, >10 years)
- Total number of depressive episodes to date
- Duration of current episode
- Family history of psychiatric disorder (yes, no, unknown) and subcategories
- Number of previous treatment failures in the current episode (<3, >=3)
- Baseline medication*
 - Selective Serotonin reuptake inhibitor (SSRI)
 - Serotonin and norepinephrine reuptake inhibitor (SNRI)
 - Antidepressant with adjunctive medications

*Baseline medication is defined as medication taken on Day 1.

D. Medical History

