In the case where a second (repeat) measurement was taken for a particular timepoint, only the second (repeat) measure will be included for analysis and the first measure will not be analyzed.

For the following 12-lead ECG parameters, summaries of values and its changes from baseline will be presented by treatment group for each scheduled assessment timepoint, beginning with the Baseline visit.

- Heart rate
- PR interval
- QRS interval
- QT interval (uncorrected)
- QT interval corrected with Fridericia's formula (QTcF)

A separate summary table will provide the number and percentage of subjects meeting the following criteria post-baseline. For this analysis, any ECG performed on unscheduled analysis visits will be included for analysis. However, any initial measurement which was superseded by a repeat measurement within the same analysis timepoint would NOT be included for this analysis.

- Absolute QTcF interval prolongation:
 - QTcF interval \geq 450 msec
 - QTcF interval \geq 480 msec
 - QTcF interval \geq 500 msec
- Change from baseline in QTcF interval:
 - QTcF interval increase from baseline \geq 30 msec

- QTcF interval increase from baseline \geq 60 msec

In the case where a subject reports qualifying records (ie, ignoring superseded initial readings) of both Abnormality with Clinical Significance and Abnormality without Clinical Significance at different analysis timepoints in a post-baseline period, the most severe record (ie, abnormality with clinical significance) will be selected for summarization.

A listing of all ECG measures will be presented.

H. Prior and Concomitant Therapy

Concomitant therapy is defined as any therapy with a start date after or on the date of the study treatment and continuing after the study treatment (ie, including up to the second follow-up visit or ongoing). Any therapy with a start date after the second follow-up visit will not be considered a concomitant therapy.

Any therapy which started prior to the infusion of study treatment is defined as a *prior* therapy. For the imputation of missing therapy dates in the categorization of prior vs concomitant status, refer to [Section XI.A Missing or Partial Date Imputation](#).

Concomitant medications will be coded using World Health Organization (WHO) Drug version September 2020 or higher coding dictionary and will be summarized by the anatomical main class (1st level) of each coded medication and, within that, the preferred name of the coded medication.

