Subjects are counted only once in each therapeutic class category. Prior and concomitant medications will be summarized separately and tabulated for each treatment group using frequencies and percentages. Percentages will be based on the number of subjects in each treatment group. Prior and concomitant medications and therapies will be listed by subject.

I. Assessments of Alertness/Sedations and other Safety Rating Scales

For the following rating scales, summaries of actual values (total scores) and changes from baseline will be presented by treatment group for each scheduled assessment timepoint, beginning with the Baseline visit.

A listing displaying the scores for these scales (individual items and total) will be provided by subject.

- Modified Observer's Assessment of Alertness/Sedation (MOAA/S)
- Clinician-Administered Dissociative States Scale (CADSS)
- Brief Psychiatric Rating Scale - Modified 4 Components (BPRS+)

The 5-Dimensional Altered States of Consciousness Rating Scale (5D-ASC) is only assessed post-baseline and for only one (1) time during the study. A listing displaying the details of the 5D-ASC will be provided by subject.

J. Others

Any other assessments which were not described in any previous sections will be listed based on the FAS. This includes (and not limited to) the following:

- Non-compliance in inclusion or exclusion criteria
- Massachusetts General Hospital Antidepressant Response Questionnaire (MGH-ATRQ)
- Mini-International Neuropsychiatric Interview (MINI)

IX. Interim Analysis

No interim analysis is planned.

X. References

XI. Appendices

A. Missing or Partial Date Imputation

For records with missing AE onset/resolution date, the following procedure will be employed for use in determining whether the AE is treatment emergent:

- AE onset dates with missing day and non-missing month will be assumed to occur on the first day of the non-missing month, except for AEs occurring in the month and year of first dosing, in which case the date will be imputed using the date of first dosing.

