- AE onset dates with missing day and month will be assumed to occur on the first day of the non-missing year (ie, January 1), except for AEs occurring in the year of first dosing, in which case the date will be imputed using the date of the first dosing.
- AEs that are not ongoing and have a resolution date with missing day and non-missing month, they will be assumed to occur on the last day of the

month, except when the end of study date or date of death is prior to the last day of the month. The date will be imputed as end of study date, or death date, whichever happens the earliest.

- AEs that are not ongoing and have a resolution date with end date month missing, the imputed end date should be set to the last day of the year 31DECYYYY, except when the end of study date or date of death is prior to the last day of the year. The date will be imputed as end of study date, or death date, whichever happens the earliest.
- If subjects died during the study and experience AEs at the time of death, the AEs that lead to death will use death date as the AE end date, otherwise, AEs that did not lead to death will be reported as ongoing.

For records with a missing therapy start and/or stop date, the following procedure will be employed for use in determining whether the therapy is prior or concomitant:

- Therapy start dates with a missing day and non-missing month will be assumed to occur on the first day of the non-missing month.
- Therapy start dates with missing day and month will be assumed to occur on the first day of the non-missing year (ie, January 1), except for therapies occurring in the year of first dosing, in which case the date will be the date of first dosing.
- Therapies that are not ongoing and have a stop date with a missing day and non-missing month will be assumed to occur on the earlier of the last day of the non-missing month or the date of death (if applicable).
- Therapies that are not ongoing and have a stop date with missing day and month will be assumed to occur on the earlier of the last day of the nonmissing year (ie, December 31) or the date of death (if applicable).
- Therapies that are not ongoing but do not have a stop date will be assumed to occur on the earlier of the last day of the non-missing year (ie, December 31) or the date of death (if applicable)

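### The SAP's definition of concomitant therapy leaves out drugs started before dosing and still being taken, so the required background antidepressants are tabulated only as prior therapy

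*SAP*

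**What the plan says.** SAP VIII.H (Prior and Concomitant Therapy) gives two definitions.

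- Concomitant: "Concomitant therapy is defined as any therapy with a start date after or on the date of the study treatment". The sentence then adds a second condition, so that both must be met: "and continuing after the study treatment (ie, including up to the second follow-up visit or ongoing".
- Prior: the definition opens "Any therapy which started prior to the infusion of study treatment is defined as a", and the label it goes on to give is prior. Nothing is said about whether the therapy has stopped.

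The same section then plans two tables: "Prior and concomitant medications will be summarized separately and tabulated for each treatment group using frequencies and percentages".

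SAP XI.A supplies the dates where they are incomplete. If the month is known: "Therapy start dates with a missing day and non-missing month will be assumed to occur on the first day of the non-missing month". If only the year is known and it is the year of dosing, the start becomes the dosing date. XI.A also imputes stop dates, and says that the whole procedure serves to decide prior versus concomitant status.

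The protocol fixes the background treatment. Inclusion criterion 7 (section 5.1) reads: "Must be on stable oral antidepressant treatment without a dose change for at least 30 days before screening". Exclusion 13b allows certain stable adjunct antipsychotics, 13c excludes recent psychotropic changes, and section 6.5 allows benzodiazepines within limits.

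**The concern.** The trial tests a single infusion given on top of an existing antidepressant. A concomitant-medication table is normally read as showing what subjects were taking while they were treated and assessed. As defined, this one shows only what was newly started. Drugs that could bear on sedation scores or on MADRS, such as a continuing benzodiazepine or adjunct antipsychotic, go into the prior table alongside drugs stopped before the study. No planned summary table would then show, by arm, all medication in use during the 24-hour assessment period. Concomitant therapies are a named item under the safety objective in SAP Table 1, so this is a planned output and not an incidental one.

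The definition also differs from the protocol's use of the term. Protocol section 6.5 records concomitant therapies from consent onward, including drugs already being taken at enrolment. Appendix 6 lists continuous antidepressants (except MAOIs), four stable antipsychotics and benzodiazepines (except clobazam) among permitted concomitant medications.

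**Working it through.** No figure in the plan needs reproducing. The check applies the SAP rule to the latest start dates that the protocol allows.

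**Inputs**
- Minimum stable period before screening: 30 days (Protocol 5.1, criterion 7).
- Screening window: "screening (up to 2 weeks [Day -15 to Day -2" (Protocol 4.1). Admission is on the evening of Day -1 and infusion the next morning on Day 1, so there is no Day 0. Screening is therefore 2 to 15 days before dosing.
- Planned subjects: 93, all of whom must meet criterion 7.

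**Step 1. Latest possible start of the required antidepressant**

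Days before dosing = (days from screening to dosing) + 30.
- Screening on Day -2: 2 + 30 = 32 days.
- Screening on Day -15: 15 + 30 = 45 days.

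In both cases the start precedes the infusion, so the drug is prior and fails the first condition for concomitant. With complete dates the concomitant table counts 0 of 93 for this drug. Exclusion 13c bars changes of psychotropic type or dose in the 30 days before screening, so the same arithmetic covers adjunct antipsychotics and benzodiazepines already in use at screening. A drug begun between screening and dosing is also prior.

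**Step 2. Compare with an overlap rule**

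Overlap rule: concomitant if the start is no later than the second follow-up visit, and the drug is either ongoing or stopped on or after dosing. Take dosing on 15 September 2022 as an illustration.

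| Therapy | Date used | SAP VIII.H with XI.A | Overlap rule |
|---|---|---|---|
| Antidepressant begun 32 days before dosing, ongoing | 14 August | prior only | concomitant |
| Antidepressant begun 45 days before dosing, ongoing | 1 August | prior only | concomitant |
| Ongoing antidepressant, start known only as 2022 | 15 September (imputed) | concomitant | concomitant |
| Drug begun after dosing, start known only as September | 1 September (imputed) | prior only | concomitant |

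**Step 3. What the partial-date rules add**

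The two rules push in opposite directions. The year-only rule can make a long-standing antidepressant concomitant by artefact. The month-only rule can make a drug begun after dosing prior, unless dosing fell on the first of the month. The month-only rule does not rescue the required antidepressant: 32 days is longer than any month, so its true start month is earlier than the dosing month. The same drug can therefore sit in different tables for different subjects according to how complete the date is. XI.A's adverse-event rule has an exception for the month of dosing, and the therapy rule has none.

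**Step 4. Consistency within the SAP**

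A rule that sends every pre-infusion start to prior needs no stop date to classify those drugs, yet XI.A imputes stop dates for that stated purpose. This suggests that overlap with treatment was intended. The two definitions also use different reference points (dosing date and infusion), so a drug begun on Day 1 before the infusion and continued meets both.

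**The case against.** The strongest reply is that nothing disappears from the report. Drugs begun earlier are in the prior table by arm and in the by-subject listings. Antidepressant classes, with or without adjuncts, are in the baseline-medication table of SAP VI.C. The added condition about continuing, the imputed stop dates and protocol Appendix 6 suggest loose drafting and not a deliberate choice. Partial start dates should be few: protocol 6.5 requires start and end dates, and SAP V.C.2 says that missing dates will be queried. All of this stands, and it limits the point to a descriptive table that is wrong as defined.

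Two stronger readings are tempting, and the documents do not support them.

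- A reader might infer that the report would suggest near monotherapy, or would hide the background drugs. That could follow only from reading the concomitant table alone. The prior table should show essentially every subject on an antidepressant, and the baseline-medication table sits beside it.
- A reader might infer from "Baseline medication is defined as medication taken on Day 1" (SAP VI.C) that rescue drugs given after the infusion count as baseline, so that treatment could affect the subgroups in SAP V.H. But VI.C opens by restricting subject characteristics to data collected before dosing. The listed classes are SSRI, SNRI and antidepressant with adjunctive medications, and no SAP text places rescue drugs in them. The subgroup summaries are exploratory and involve no hypothesis tests.

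**Conclusion.** The definition is wrong as written and should be corrected. With complete dates, none of the 93 planned subjects' required antidepressants enters the concomitant table, nor does any adjunct antipsychotic or benzodiazepine begun before dosing and still in use. What is lost is narrow: no summary table separates drugs still in use at dosing from drugs already stopped, and for a minority of records the classification turns on date completeness.

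The count of 0 of 93 assumes that all subjects meet criterion 7, that each unbroken course is recorded once with its true start date, and that the year-only rule is not triggered. How often partial dates will occur is unknown. No estimand, primary or secondary test, or power figure depends on this classification.

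**What to change.** Amend SAP VIII.H as follows.

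- **Concomitant:** any therapy taken at any time from the start of infusion to the second follow-up visit, whatever its start date.
- **Ongoing at infusion:** a therapy begun earlier and still in use counts as both prior and concomitant, or is shown in a separate prior-and-ongoing category. State which.
- **Prior only:** a therapy stopped before the infusion.
- **Reference point:** use the start of infusion in all the definitions.

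Amend SAP XI.A so that a partial start date compatible with the month or year of dosing is set to the dosing date only when the stop date does not show that the therapy ended before dosing. Without that check, a drug begun and stopped earlier in the dosing month would receive a start after its stop and could be labelled concomitant. Under the overlap definition, an imputed start date no longer decides whether an ongoing drug is concomitant. It affects only whether the drug is also counted as prior, and querying incomplete dates remains the remedy for that.

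The cost is SAP wording and table programming. Protocol 6.5 already collects start and end dates, and SAP I.B allows changes until database lock. No new data and no protocol amendment are needed.

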6.5 Concomitant Therapy

Any medication or vaccine (including over-the-counter or prescription medicines, vitamins, and/or herbal supplements) that the subject is receiving at the time of enrollment (within 30 days before the screening visit) or receives during the study must be recorded on the CRF along with:

- Type of drug.
- Reason for use.
- Dates of administration including start and end dates.
- Dosage information including dose and frequency.
- Route of administration.

COVID-19 vaccination is allowed as long as the doses are administered \geq 30 days before the administration of study drug. Vaccination is not allowed during the course of the study.

Concomitant therapies must be recorded throughout the study beginning with the signing of the ICF (ie, screening) until the second follow-up visit. Concomitant therapies should also be recorded beyond this time only in conjunction with new or worsening AEs or SAEs. For subjects who fail screening, concomitant therapies do not need to be recorded unless there is an AE.

Modification of an effective pre-existing therapy should not be made for the explicit purpose of entering a subject into the study. The following medications are prohibited for the duration of the study beginning from 1 week (or 5 half-lives, whichever is longer) prior to Baseline (Day -1). If applicable, the possible effects of these medications on the efficacy endpoints will be considered during the assessment of the evaluable period (see [Table 6](#) in [Appendix 6](#) for further details).

- Receipt of a known potent inhibitor of hepatic cytochrome P450 (CYP) 2B6, or CYP3A, activity within 1 week or within a period 5 times the drug's half-life, whichever is longer, before the first administration of study drug on Day 1.
- Treatment with a disallowed antipsychotic within the past 30 days prior to screening, except subjects who are on stable doses of quetiapine, aripiprazole, brexpiprazole, or olanzapine prescribed as adjunct treatment for depression (without psychosis) may be included in the study.
- Any changes in psychotropic medication type or dose within the past 30 days prior to screening.
- Treatment with monoamine oxidase inhibitors (MAOIs) currently or within the past 30 days of screening.

The following medications are restricted for the duration of the study beginning from the date of the screening visit until the completion of assessments at Visit 4 (Day 15) or the discontinuation visit:

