Appendix 6 Permitted and Prohibited Concomitant Medications

Table 6 provides a list of permitted and prohibited concomitant medications throughout the study.

Drug	Episodic Use	Continuous Use	Comments
Amantadine	N	N	
Analgesics (except opiates)	Y	Y	
Anti-anginal drugs	N	N	Angina is exclusion
Anti-arrhythmics	N	N	Arrhythmia is exclusionary
Anticholinergics	N	N	
Anticholinesterase inhibitors	N	N	
Anticoagulants	N	N	
Anticonvulsants	N	N	
Antidepressants	N	Y	MAOIs are always excluded
Antidiarrheal	Y	N	
Anti-emetics	Y	N	
Anti-inflammatory	Y	Y	
Antipsychotics	N	Y	Stable doses of quetiapine, aripiprazole, olanzapine, and brexpiprazole are permitted for continuous use
Antifungals	N	N	No ketoconazole, fluconazole due to CYP3A interaction
Artemisinin			
Aspirin	Y	Y	
Benzodiazepines	Y	Y	Except clobazam Daily doses of benzodiazepine receptor agonists will be limited to 2 mg/day or less of lorazepam or equivalents. Benzodiazepines will be prohibited within 6 hours prior to dosing

Table 6 List of Permitted and Prohibited Concomitant Medications

Drug	Episodic Use	Continuous Use	Comments
Clarithromycin	N	N	CYP3A interaction
Erythromycin	N	N	CYP3A interaction
Elagolix	N	N	CYP3A interaction
Fish oils	Y	Y	
HIV drugs	N	N	HIV excluded
Hormones	N	Y	Glucocorticoids excluded due to CYP3A interaction
Itraconazole	N	N	CYP3A interaction
Ketoconazole	N	N	CYP3A interaction
Lithium	N	N	
Methyldopa	N	N	
Modafinil	N	N	
Opiates	N	N	
Oritavancin	N	N	CYP3A interaction
Pioglitazone	N	N	CYP3A interaction
Rifabutin	N	N	CYP3A interaction
Rifampin	N	N	CYP interaction
St. john's wort	N	N	CYP3A interaction
Stimulants	N	N	
Steroids (oral)	N	N	
Steroids (inhaled, topical, ophthalmic)	Y	Y	
Telithromycin	N	N	CYP3A interaction
Telotristat	N	N	CYP3A interaction
Ticlopidine	N	N	CYP2B6 interaction

Table 6 List of Permitted and Prohibited Concomitant Medications

Drug	Episodic Use	Continuous Use	Comments
Troglitazone	N	N	CYP3A interaction
Troleandomycin	N	N	CYP3A interaction
Tryptophan	N	N	
Voriconazole	N	N	CYP3A interaction

Note: Permitted episodic or continuous use of a concomitant medication is indicated with a “Y” (yes).

Prohibited episodic or continuous use of a concomitant medication is indicated with an “N” (no).

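### The SAP's concomitant-therapy definition classes background drugs that continue through dosing as prior only, so the concomitant table would omit nearly all of them

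*SAP*

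**What the plan says.** SAP VIII.H sets two rules.

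- Concomitant: "Concomitant therapy is defined as any therapy with a start date after or on the date of the study treatment and continuing" past dosing, with the window closing at the second follow-up visit.
- Prior: "Any therapy which started prior to the infusion of study treatment is defined as a" prior therapy. This rule has no condition on the stop date.

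The same section then states: "Prior and concomitant medications will be summarized separately and tabulated for each treatment group using frequencies and percentages". It also plans a by-subject listing of both groups.

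Three other places bear on how the rules work in practice.

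- Protocol 5.1, criterion 7: "Must be on stable oral antidepressant treatment without a dose change for at least 30 days before screening". Protocol Appendix 6, Table 6, allows antidepressants other than MAOIs as continuous use. For antipsychotics it says: "Stable doses of quetiapine, aripiprazole, olanzapine, and brexpiprazole are permitted for continuous use". It also allows benzodiazepines other than clobazam, within limits.
- Protocol 6.5: "Concomitant therapies must be recorded throughout the study beginning with the signing of the ICF (ie, screening) until the second follow-up visit". Start and end dates are among the items to be recorded.
- SAP XI.A introduces its imputation rules for therapy dates with: "For records with a missing therapy start and/or stop date, the following procedure will be employed for use in determining whether the therapy is prior", the alternative being concomitant. A start date with only the year known, where that year is the dosing year, is set to the date of dosing.

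**The concern.** A reader expects the concomitant table to show what subjects were taking when dosed and afterwards. Under VIII.H, for a drug that continues, the start date alone decides which table it enters. In this trial background therapy is an entry requirement, so the drugs most relevant to interpretation nearly all start before dosing and go to the prior table.

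The stake is context for the by-arm safety summaries. Sedation (MOAA/S), dissociation (CADSS), psychotic symptoms (BPRS+) and blood pressure are all summarized by treatment group, and SAP Table 1 lists concomitant therapies under the safety objective. Someone checking whether the arms were balanced on benzodiazepines or antipsychotics would find a near-empty concomitant table and could take it to mean that few subjects used them. The prior table does not settle the question, because it puts drugs stopped before dosing and drugs still being taken on the same lines.

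**Working it through.** The plan gives no figure to reproduce, so the check applies the written rules to test records.

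**Inputs.** The VIII.H definitions, the XI.A start-date imputation, and criterion 7. For illustration I assume dosing on 15 September 2022 and the second follow-up visit on 29 September 2022 (Day 15).

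**Rules as coded.**
- Prior: start before dosing.
- Concomitant (VIII.H): start on or after dosing, no later than the second follow-up visit, and either ongoing or ending on or after the dosing date. The last condition reads the continuation requirement generously.
- Concomitant (overlap): start no later than the second follow-up visit, and either ongoing or ending on or after the dosing date, whatever the start date.

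| Record | Start date after XI.A | VIII.H | Concomitant under overlap? |
|---|---|---|---|
| Full date 10 Mar 2021, ongoing | 10 Mar 2021 | prior only | yes |
| May 2022, day missing, ongoing | 1 May 2022 | prior only | yes |
| Sep 2022, day missing, ongoing | 1 Sep 2022 | prior only | yes |
| 2021 only, ongoing | 1 Jan 2021 | prior only | yes |
| 2022 only (dosing year), ongoing | 15 Sep 2022 | concomitant only | yes |
| 1 Jun 2022, stopped 1 Aug 2022 | 1 Jun 2022 | prior only | no |
| Rescue drug, Day 1 only | 15 Sep 2022 | concomitant only | yes |
| New drug from Day 6, ongoing | 20 Sep 2022 | concomitant only | yes |

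**Result.** Of the five ongoing background records, four are prior only, including the one with a complete date. The fifth is concomitant solely because its month and day are unknown. The same drug can therefore fall in either table depending on how complete its start date is.

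**Size.** An antidepressant that meets criterion 7 was at a stable dose for at least 30 days before screening, so its true start precedes dosing. With 93 planned subjects, about 93 of 93 should have such a drug ongoing at dosing. Under VIII.H it enters the concomitant table only through the year-only exception, so the expected count is close to zero.

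**Internal evidence of intent.** XI.A imputes stop dates in order to decide prior or concomitant status. Under VIII.H no stop date can move a pre-dose drug out of the prior group. For background drugs that imputation has a purpose only under an overlap rule. This is an inference about intent, not a statement in the SAP.

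**Day 1 boundary.** The concomitant rule uses the date of treatment and the prior rule uses the infusion. A drug started on Day 1 before the infusion and continued meets both definitions.

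**The case against.** The strongest reply is that little information is lost. SAP VI.C summarizes baseline medication by treatment group, defined as what was taken on Day 1, in three lines: SSRI, SNRI, and antidepressant with adjunctive medications. SAP V.H makes these subgroups, and VII.K repeats the descriptive efficacy summaries within them. All medications are listed by subject. The prior table is also less mixed than it might be: protocol 6.5 reaches back only 30 days before screening, and exclusion 13c bars psychotropic changes in those 30 days, so most antidepressants and antipsychotics in the prior table should be ongoing ones. No efficacy model, analysis set or adverse-event rule uses the classification.

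All of that stands, and it limits the impact. A reader might infer that the planned outputs cannot show at all what subjects were taking when dosed. The documents do not support that, given VI.C and the listings. What VI.C leaves out is the individual drug, a separate line for antipsychotics or benzodiazepines, and anything about use during follow-up.

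Three other stronger readings also fail.

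- That every background drug is excluded on start date alone. VIII.H also has the continuation condition, and XI.A creates the year-only exception.
- That a single rescue dose given and finished during the infusion belongs to neither table. This needs a strict reading of the continuation condition. The wording is ambiguous, and a reasonable programmer would class such a dose as concomitant.
- That VIII.H contradicts protocol 6.5. That section is a recording rule, and protocol 9.4.3 asks only for separate summaries without drawing the boundary.

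**Conclusion.** Wrong as written, low impact. Followed literally, VIII.H leaves nearly all background antidepressants out of the concomitant table, together with ongoing permitted antipsychotics and benzodiazepines, and it splits identical drugs by date completeness. This is a stated rule that gives the wrong result, not a missing detail.

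The estimate of about 93 of 93 subjects on an antidepressant at dosing against close to zero in the table assumes that criterion 7 is met, that the antidepressant is not stopped between screening and dosing, that it is held as one record with its true start date, and that few start dates are known only as the dosing year. The plan does not say how many subjects will take antipsychotics or benzodiazepines, so their omission cannot be sized.

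The consequence stays within the descriptive medication tables. A reader might infer some effect on the primary or secondary efficacy results; nothing in the SAP links this classification to them.

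**What to change.** In SAP VIII.H:

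- Define prior as stopped before dosing.
- Define concomitant as taken at any time from dosing to the second follow-up visit, whatever the start date, including single doses on Day 1. Protocol 6.5 lists dates of administration but not clock times, so classify Day 1 records by date where no time is recorded.
- In the concomitant table, show drugs started before dosing and ongoing separately from drugs started on or after dosing, so that new post-dose medication stays visible.

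In SAP XI.A, change the year-only rule so that an ongoing drug with a partial start date is not moved to the started-on-or-after-dosing group by imputation alone. Without this, the exception would carry over into the new split.

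The cost is a few sentences in the SAP and one change to the derivation program. Start and end dates are already collected under protocol 6.5, and SAP I.B allows changes until database lock.
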